**C.13. Testing Specific Aim 3 (predicting individual differences in therapeutic benefit)**

All tests of Specific Aim 3 will focus on data from the MT group only.

a. Testing predicted relationships between processes underlying MT and MT benefit using lesion location: We will examine the relationship between the change in primary and secondary outcome measures and lesion location using whole-brain voxel-based lesion-symptom mapping (VLSM) analyses [83]. VLSM measures whether a behavioral score systematically differs between participants with and without damage to each voxel under investigation. Tests of this difference use a t-statistic to describe the difference in means between the damaged-group and non-damaged-group while taking into account the variances within each group. The t-statistic is thus used as a convenient measure of group differences, without the intention of comparing it to the parametric t distribution. Instead, statistical significance will be determined by non-parametric permutation tests [84], in which the distribution used for inferential statistic calculations are created by sampling from the observed data rather than assuming an a priori distribution. Thresholds for significance will be calculated from the 95th percentile of this distribution, to ensure a family-wise false positive rate of 0.05 [84]. The total number of comparisons will also be reduced by only performing analyses on those voxels that are damaged in at least 10% of participants (to avoid undue influence of a small number of participants).

As in the previous measures, we will use an ANCOVA-like procedure to determine whether post-treatment scores (the DV) are affected by damage status to each individual voxel under consideration (the IV) after controlling for pre-treatment score and total lesion volume (covariates). Separate VLSM analyses will be done for each primary and secondary outcome

Albert Einstein Healthcare Network Einstein	AEHN Protocol/Summary		
	NUMBER	DATE	PAGE
	HRP-204	11/1/2011	16 of 27

measure. The voxels identified as being predictive of MT benefit using the VLSM analysis should be consistent with the a priori ROI predictions (Table 1). VLSM will also allow us to test whether voxels outside of these ROIs predict MT benefit.

- b. Testing predicted relationships between processes underlying MT and MT benefit using behavioral scores: In addition to using VLSM to test how the proposed neural substrates of the four sensorimotor processes are able to predict MT's benefit, we will also use the confirmatory behavioral measures (our proxy for the integrity of the processes) to predict MT's benefit. We will use linear stepwise regression to predict post-treatment scores (the DV) using each behavioral measure (the second level predictor/ IV) after controlling for pre-treatment score (the first level predictor/ IV). Note that this analysis is identical to the ANCOVAs used above except that a continuous IV is used, thus requiring regression rather than ANOVA. Analyses will be done separately for each of the four processes and each primary and secondary outcome measure. Testing our predictions about the processes will involve examining the sign and significance of second level predictor's regression weight. For example, if poor proprioception leads to reduced benefit of MT (see B.2), the regression weight for RASP (where high score corresponds to better proprioception) will be significantly positive. Alternatively, if poor proprioception lead to increased benefit of MT, the regression weight will be significantly negative. Finally, if proprioception does not affect MT benefit, the regression weight will not significantly differ from zero. Determining the influence of action observation, visual-proprioception integration, and motor imagery will use the same logic.
- c. Testing predicted relationships between lesion areas and confirmatory behavioral measures  
As summarized in Table 1, we predict that damage to particular ROIs will cause deficits in particular sensorimotor processes, which we will assess using the confirmatory behavioral tests. We will test these predictions in two ways. First, we will use t-tests to determine whether the pre-treatment confirmatory behavioral tests (the only time the tests are administered) will differ as a function of damage status to a particular ROI (using a 20% of volume criteria). Second, we will use linear stepwise regression to predict behavioral measure scores using percent damage to each predicted ROI after first controlling for total lesion volume. We have previously used both approaches successfully in a study of action observation [68].
- iii. Describe where and how data will be stored locally: All computerized data will be password protected and stored only on the network share drive. Paper copies of data will be kept in locked filing cabinets in research staff members' offices.
- iv. Specify how long data will be stored locally: 6 years
- v. Specify who will have access to the data locally: Only research personnel listed on the Application for Human Research.
- vi. Describe process that will be followed to ensure accuracy of collected data: Collected data that is entered into computer databases/spreadsheets will regularly be checked by research staff for data entry errors. Any errors will be discussed, reconciled, and the data re-entered on the spreadsheet.
- vii. Will data be sent out or received:  No  Yes

Albert Einstein Healthcare Network Einstein	AEHN Protocol/Summary		
	NUMBER	DATE	PAGE
	HRP-204	11/1/2011	17 of 27

- a. Who is responsible for receipt or transmission of the data? The research assistant (RA).
- b. How will the data be transported? Brain scan data (MRI or CT) on a DVD will be transferred from the University of Pennsylvania to the Medical Arts Building of the Elkins Park Campus by the RA. Password protected files transported will also be transported via Groupwise Email.
- h. Provisions to monitor the data for the safety of subjects (Required only when Human Research involves more than minimal risk):**
  - i. Describe plans to periodically evaluate the data collected regarding both harms and benefits to determine whether subjects remain safe. Include what data will be reviewed, who will review the data and when the data will be reviewed: N/A
- i. Withdrawal of Subjects:**
  - i. Describe the anticipated circumstances under which subjects will be withdrawn from the research without their consent: Participants will be withdrawn without their consent only if it is determined, after consent, that they no longer meet study criteria, or if it becomes apparent that the study is causing the participant undue fatigue or frustration.
  - ii. Describe the procedures that will be followed when subjects withdraw from the research (or request that their data be withdrawn), including partial withdrawal from procedures with continued data collection: Following a participant's withdrawal or request for data withdrawal, no new information about that participant is collected. Data already gathered are retained and, if appropriate, used in the group analysis. Participants are informed of this in the consent form.

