#### B.1. Understanding individual patient differences in treatment response

A critical, but often understudied, issue in rehabilitation is predicting individual patient differences in treatment response. As reviewed in section A.1, a wide range of therapies exist for the treatment of hemiparesis, and several recent RCTs comparing two active treatments have reported equivalent benefits at the group level [9, 30, 31]. It would be clinically valuable to understand the characteristics of patients who do and do not respond to each therapy given the magnitude of these individual differences. For example, in a recent RCT of MT for chronic stroke patients [20], improvement in the Brunnstrom scale outcome measure ranged from 0% to 33% (estimated from two standard deviation above and below the mean of 16.5% improvement). Information about predicted individual differences would be useful for clinicians when deciding the course of treatment most likely to benefit the patient.

We assert that individual differences in response to MT are predictable through an understanding of the mechanisms responsible for MT's therapeutic benefit. The assembled team composed of researchers trained in the basic science of sensorimotor control ([name]) and its application to stroke patients (Drs. [name], [name], and [name]) is uniquely positioned to address this issue. The project is innovative because it will test competing predictions regarding the mechanism of MT by utilizing individual differences in lesion location and the integrity of four sensorimotor processes that may underlie MT's benefit. As an overview, we will first discuss the four sensorimotor processes that may underlie the mechanisms of MT's benefit (B.2), and then proceed to a summary of the

Albert Einstein Healthcare Network <hr/> Einstein	AEHN Protocol/Summary		
	NUMBER	DATE	PAGE
	HRP-204	11/1/2011	4 of 27

neural substrates that subserve these processes (B.3). Following this will be a discussion of the behavioral tasks we will use as convergent validity tests of the neuroanatomic predictions (B.4). Finally, we will summarize all of these predictions in Table 1.

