
In addition to action observation, proprioceptive feedback is relied upon during MT. The most obvious prediction is that poor proprioception would lead to poor response to MT, just as it does in other therapies [37]. This outcome would be logical because proprioception is the only source of sensory feedback about the hidden impaired limb during MT (since vision of that limb is blocked). The perceptual-motor system may require some form of feedback to recognize that the movement of the impaired limb does not match the visual feedback, and thus the system must modify the motor command to more closely match the visual feedback about the unimpaired arm. Without that feedback, adjustment of the perceptual-motor system might not occur. The alternative, and more counter-intuitive, prediction is that intact proprioception might disrupt MT. Our reasoning is that MT sets up a conflict between the proprioception signal coming from the impaired arm and the visual feedback about the mirror-reflected unimpaired limb. The presence of a veridical proprioception signal from the impaired arm may disrupt the effects of the false visual feedback. Support for this second prediction comes from other studies in which proprioceptive feedback is actively suppressed when the to-be-learned task involves a conflict between vision and proprioception [38]. If this counterintuitive prediction is verified, it would be especially noteworthy because poor proprioception often leads to poor recovery with standard therapies. Advancing a therapy that would benefit patients who respond poorly to other therapies is particularly innovative and significant. The proposed study will be able to differentiate between these two possibilities by using a behavioral assessment of proprioception to determine whether disrupted proprioception is associated with greater or reduced benefit of MT (see C.13).

Albert Einstein Healthcare Network <hr/> Einstein	AEHN Protocol/Summary		
	NUMBER	DATE	PAGE
	HRP-204	11/1/2011	5 of 27

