Finally, a previous study of MT [18] hypothesized that removing visual feedback of the impaired arm causes the perceptual-motor system to try to fill in that information using motor imagery. Given that other forms of motor imagery can be therapeutically beneficial, the authors proposed that motor imagery was similarly beneficial in MT. Data from a later RCT of mirror therapy calls this claim into question [20]. When MT was compared to the same therapy with a covered mirror, the results clearly indicated that MT benefited patients while the covered mirror therapy did not. However, in both forms of therapy vision of the impaired limb was blocked, and thus motor imagery would be called upon in both. We will test whether MT's benefit is predicted by motor imagery ability (see C.13 for details).

In summary, we will test competing predictions about the mechanism of MT by utilizing individual differences in the integrity of four sensorimotor processes (action observation, proprioceptive feedback, visual/proprioceptive integration, and motor imagery) that may underlie MT's benefit.

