### B. 4. Converging evidence between lesion location and other behavioral tests

In addition to making predictions about the integrity of the four processes that may underlie MT's benefit based on lesion location, we will measure performance on confirmatory behavioral tests to (1) provide further evidence about the neural substrates of these functions and (2) allow clinicians to have simple behavioral tests to predict individual differences in MT response without having to rely on lesion location information. All behavioral tests have been previously used in our labs. For action observation, we will use a test that involves viewing sequentially presented video pairs of actions, with the patient making same/different judgments about the actions [68]. For proprioceptive feedback, we will use the RASP [69], a standard clinical measure of proprioception that will also be a primary outcome measure. For visual-proprioceptive feedback, we will use a visual-analogue scale of initial mirror illusion sensation (rate how strongly it feels as if the arm you see in the mirror is actually the arm behind the mirror) and a simple judgment task (Parson's task [70]) that has been shown to require integration of visual and proprioceptive input. In this task, patients judge whether a visually presented hand is a left or right hand. These judgments are affected by the orientation of the participant's own hand, suggesting the decision is based on the seen and felt position of the body. We will have patients make verbal judgments while we systematically manipulate the orientation of the patients' hand. Finally, motor imagery will be assessed using consistency

Albert Einstein Healthcare Network Einstein	AEHN Protocol/Summary		
	NUMBER	DATE	PAGE
	HRP-204	11/1/2011	6 of 27

on a grasping imagery task [71] in which patients report how they imagine they would grasp a handle (overhand or underhand) and compare the imagined results to their actual grasping of an object. Table 1 summarizes the preceding three sections.

PROCESS	NEURAL SUBSTRATE	CONFIRMATORY BEHAVIORAL TEST
Action observation	IFG, IPL, pMTG	Spatial action recognition task
Proprioceptive feedback	SI, SII	RASP
Visual-proprioceptive integration	IPL, BA5	Parson's task, screening questionnaire
Motor imagery	IPL, BG, PM	Imagined grasping

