#### C.7. THERAPY REGIMEN

**a. Group assignment:** A research assistant (RA), who will not be involved in any assessments, will assign patients to the MT or placebo therapy (identical therapy with an opaque divider rather than a mirror) using stratified randomization based on the patient's Fugl-Meyer score. Before starting the trial an assignment order will be developed based on whether a patient's pre-treatment Fugl-Meyer score was low (between 10 and 30) or moderate (between 30 and 50). A previous MT RCT using a similarly chronic patient population and an identical placebo therapy showed little benefit of the placebo therapy. Thus, we must consider a balance between the scientific requirements of an appropriate control group and the ethical considerations of using patients' time to complete a therapy that is known to be ineffective. To balance these considerations, we will assign patients to the MT and placebo treatment groups in a 2:1 ratio, respectively. This inequality in sample size will only reduce statistical power by approximately 3% [81]. In addition, patients assigned to placebo treatment will be given the option of being crossed over to receive MT after the three month assessment. Patients will not be aware of which therapy is the placebo because both therapies will be described as studying the role of visual feedback rather than a test of "mirror therapy." Both treatments will include 2 daily 30 minute

Albert Einstein Healthcare Network <hr/> Einstein	AEHN Protocol/Summary		
	NUMBER	DATE	PAGE
	HRP-204	11/1/2011	12 of 27

therapy sessions, 5 days per week over a 4 week period.

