**C.12. Testing Specific Aim 2 (optimal treatment dosing)**

Optimal treatment dosing will be examined by expressing each primary outcome measure's average value at the three mid-treatment assessments and the three-month post-treatment assessment as a percentage between pre-treatment (0%) and immediate post-treatment (100%) assessments. This information could then be used in clinical decision-making when determining whether the magnitude of change expected in a given time period would be "worth" the additional treatment time or whether that addition time would be better spent trying another therapy. Inferential tests will not be used because of the problem of being unable to detect "non-significant" differences between two time points as well as the possibility that the large sample size will be able to detect statistically-significant differences across adjacent time points even though the clinical significance of the differences' magnitudes are questionable.

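### C.13 analyses only the MT arm, which supports prediction of outcome under MT but not the mirror-specific reading that C.13.b places on its regression weights

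*Combined protocol and SAP*

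**What the plan says.** C.13 opens with the restriction "All tests of Specific Aim 3 will focus on data from the MT group only". C.13.b regresses post-treatment score on pre-treatment score and one behavioural measure, separately for each process and outcome, and judges the process by the direction and significance of the weight. Proprioception is the worked example. A positive weight would mean that poor proprioception reduces benefit and a negative one that it increases benefit. The third case reads: "if proprioception does not affect MT benefit, the regression weight will not significantly differ from zero". The other three processes follow the same reasoning. C.13.a fits a comparable adjusted model voxel by voxel and treats the voxels it finds as predictors of MT benefit.

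Two purposes are stated. B.1 says of the project that "it will test competing predictions regarding the mechanism of MT by utilizing individual differences in lesion location" and the integrity of the four processes, and B.2 closes in the same terms. B.4 gives a practical purpose: to "allow clinicians to have simple behavioral tests to predict individual differences in MT response". The plan contains no placebo-arm slope and no therapy-by-predictor term.

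**The concern.** The placebo is the same exercise programme with an opaque divider in place of the mirror. A patient characteristic may go with improvement because it predicts response to exercise, change over time or gain from retesting, with no part played by the mirror. With one arm, this cannot be told apart from a characteristic that matters because of the mirror.

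The plan's own background makes a non-specific association plausible, though it does not show one. B.2 expects that "poor proprioception would lead to poor response to MT, just as it does in other therapies". On motor imagery, B.2 says of an earlier trial with a covered-mirror control that "in both forms of therapy vision of the impaired limb was blocked, and thus motor imagery would be called upon in both", and uses that contrast between arms to question imagery as the mechanism. C.13 then does without that contrast.

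Two wrong conclusions could follow. A general prognostic factor could be reported as support for one of the four mechanisms, and a missed association could be reported as evidence against one.

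**Working it through.** **1. What the weight estimates.** Let γ₁ be the predictor's slope on post-treatment score under MT, given pre-treatment score, and γ₀ the same slope under placebo. The MT-only regression estimates

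γ₁ = γ₀ + (γ₁ − γ₀).

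The predictor's effect on the MT-minus-placebo difference is γ₁ − γ₀. The MT-only weight equals it only if γ₀ = 0. Adjusting for pre-treatment score does not make γ₀ zero.

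**2. Figures in the plan.** None concerns Aim 3. The only power statement (C.7.a) is that 2:1 allocation costs about 3%, which relates to the comparison of therapies. With 100 patients and two-sided 0.05, power is Φ(δ/[σ√(1/n₁+1/n₂)] − 1.96). Moving from 50/50 to 66.7/33.3 costs 4.8, 3.7 and 2.5 percentage points when 1:1 power is 80%, 90% and 95%. The stated figure is therefore reasonable at high base power, but it says nothing about slopes.

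**3. Inputs for the illustration.** From the plan: 100 patients at 2:1, so about 67 and 33. Assumed, because the documents are silent: no dropout, two-sided 0.05, normal errors, MT-arm partial r of 0.2, 0.3 or 0.4, and a placebo slope that is equal, half or zero. Partial r converts to residual SD per predictor SD by r/√(1−r²), giving 0.204, 0.314 and 0.436. The two-arm model is post = pre + therapy + predictor + therapy × pre + therapy × predictor.

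**4. Simulated rejection rates.**

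| | r = 0.2 | r = 0.3 | r = 0.4 |
|---|---|---|---|
| MT-only test, any placebo slope | about 36% | about 70% | about 92% |
| Interaction, equal slopes | about 5% | about 5% | about 5% |
| Interaction, zero placebo slope | 13–16% | 27–31% | 43–51% |
| Interaction, half placebo slope | 7–9% | 10–13% | 15–19% |

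The ranges cover several assumed baseline–post and predictor–baseline correlations. The first row is the same for every placebo slope because the MT-only test never sees placebo data. The reverse error also occurs: with an MT slope of 0 and a placebo slope of −0.314, the predictor does modify the MT–placebo difference, yet the MT-only test rejects in only 5%.

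**5. Precision of the difference.** The large-sample ratio of standard errors, interaction to MT-only, is √(1/67 + 1/33)/√(1/67) = √(100/33) = 1.74. In simulation it is about 1.8. The 95% CI half-widths are about 0.44 and 0.25 residual SD per predictor SD.

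**6. What non-significance excludes.** The MT-only test misses 100 − 36 = 64%, 100 − 70 = 30% and 100 − 92 = 8% of associations at the three sizes. An estimate of exactly zero has an interval of ±0.25, which still contains 0.204. Any non-significant estimate between about 0.314 − 0.25 = 0.06 and 0.25 has an interval that contains 0.314. C.12 shows awareness of a related problem: it begins "Inferential tests will not be used because of the problem of being unable to detect" and goes on to refer to non-significant differences.

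**7. The therapy × pre term.** With no predictor effect in either arm and residual SD 0.6, leaving the term out gives false rejection of about 14% and 34% at predictor–baseline correlations of 0.4 and 0.7 if baseline slopes are 0.9 and 0.6. With slopes of 0.8 and 0.7 it is about 6% and 8%. With the term included it is about 5% throughout. All these slopes are assumed.

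**The case against.** The strongest reply is that Aim 3 is about prediction. The stated goal is to understand individual differences and assess predictors of benefit, and C.13 is titled accordingly. For that use MT-only data are right, and this stands. A reader might infer that the Aim 3 analyses are invalid as a whole; B.4 does not support that. What does not stand is the further step to mechanism, which B.1 and B.2 state and C.13.b carries out.

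A second reply is that the placebo is inert, since C.7.a reports that "an identical placebo therapy showed little benefit of the placebo therapy". That is a group-level result from an earlier trial. A small mean change does not make the slope of change on a predictor zero.

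Third, a reader might infer that the plan declares non-significance to be proof of no effect. It does not. The sentence runs forward, from no effect to a non-significant weight. The reverse inference is implied, because this is one of three outcomes by which each process is judged.

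Fourth, the explicit reading of signs and significance is confined to C.13.b. C.13.a has the same limitation in milder form.

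Fifth, the interaction has low power and cannot settle every mechanism question. A process that works equally in both arms, as B.2 suggests for imagery, gives no interaction whether or not it contributes to improvement. This stands, and it is why the placebo slope must be reported beside the difference. Low power limits what may be claimed; it does not make the MT-only weight answer the question.

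Finally, the ambiguity falls mainly on weights in the direction of general prognosis. A negative weight for proprioception, the plan's distinctive prediction, is harder to explain that way.

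**Conclusion.** The concern holds for the mirror-specific and mechanistic reading of MT-only associations, chiefly in C.13.b, and for the implied reading of a non-significant weight. It should be corrected before the data are analysed. The identification point needs no numerical assumption: an MT-only weight equals the mirror-specific one only if the placebo slope is zero, and the documents do not establish that. The sizes are illustrative and rest on a 67/33 split, no dropout and assumed effect sizes.

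The documents do not show that any of the four predictors is in fact non-specific; they only make it plausible for proprioception and imagery. Nor do they show that baseline slopes differ by arm, so the therapy × pre term is a sensible precaution and not an established need. Aim 1, the lesion–behaviour analyses of C.13.c (pre-treatment tests only) and prediction of outcome under MT are unaffected.

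**What to change.** 1. Keep the MT-only regressions and the voxel-based analyses, and label them as predictors of outcome under MT.
2. For behavioural predictors measured before assignment, add an exploratory model in all randomised patients: post = pre + therapy + predictor + therapy × pre + therapy × predictor. Report the MT slope, the placebo slope and their difference, each with a 95% CI. Base any mirror-specific claim on the difference. State that a difference near zero does not show that the process plays no role in improvement.
3. State in C.13.b that a non-significant weight is inconclusive and will be reported as an estimate with its CI.

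The cost is SAP wording and one added model. C.5 places the Table 1 tests before assignment, and both post-treatment assessments precede the optional crossover, so little or no new testing is needed. The mirror-illusion rating should enter only if it is collected before assignment in both arms: Table 1 lists a screening questionnaire, but the summary of tests in 6.e.iii does not mention the rating. A similar interaction for the lesion regions is optional and limited to patients with scans.

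The drawback is precision. With a standard error about 1.8 times that of the MT-only slope and power of about 14%, 28% and 49% at partial r of 0.2, 0.3 and 0.4 (zero placebo slope), many differences will be inconclusive. The interaction tests should be labelled exploratory and unadjusted. The number of tests, and the use of RASP as both covariate and predictor, are separate points.

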##### b. For prospective studies:

i.) Total number of subjects planned to be enrolled in the study at AEHN site(s): 140 screened in single session, with target of 100 meeting inclusion criteria for the full treatment study

ii) For multi-site projects, please indicate total number of subjects planned to be enrolled in the study at all sites: Of the 100 participants that will meet inclusion criteria for the full treatment study, approximately 60 will be recruited to the brain imaging (including both MRI and CT) study conducted at U. Penn. The rest will have already received brain scans through their

Albert Einstein Healthcare Network Einstein	AEHN Protocol/Summary		
	NUMBER	DATE	PAGE
	HRP-204	11/1/2011	7 of 27

participation in MMRI sponsored studies included the Moss Research Registry and conducted via the "Cognition and Action" or "Language and Aphasia" laboratories.

iii) Describe access to a population that would allow recruitment of the targeted number of subjects (*i.e. how many potential subjects do you have access to? What percentage of those potential subjects do you need to recruit?*) : Patients and controls will be recruited from the Moss Research Registry; the requisite approval has been obtained from Registry Coordinator. The registry contains medical records of patients who have already agreed to participate in studies, allowing us to pre-select patients based on the likelihood of meeting inclusion criteria. Patients will also be recruited using a flyer distributed by therapists in the clinical programs at MossRehab and by the research staff to participants in stroke support groups in the Philadelphia metropolitan area.

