#### e. Human Research Methods:

- i. Describe and explain the study design (*e.g. randomized, double-blind, placebo-controlled clinical trial or retrospective chart review*): randomized, placebo-controlled clinical trial
- ii. Describe all research activities involved in this protocol, including a study visit timeline if appropriate: C.5. PRE-TREATMENT ASSESSMENT: Should the patient meet the inclusion criteria, an additional battery of pre-treatment assessment tests will be completed as the first measure of the primary and secondary outcome measures. The primary outcome measures will be the (1) Fugl-Meyer test, described above, (2), Action Research Arm Test (ARAT), a valid and reliable measure of arm function in simulated ADLs, (3) the Rivermead Assessment of Somatosensory Performance (RASP), which tests proprioception, two-point discrimination, surface pressure touch, surface localization, and tactile extinction [121], and (4) in right hemisphere patients only, a virtual-reality assessment of navigation (VRLAT) developed by [name] [77], which is more sensitive to mild forms of hemispatial neglect than paper-and-pencil tests. Secondary outcome measures will be (1) Stroke Impact Scale [76], (2) timed finger tapping, (3) maximum grip and pinch force, as assessed using a dynamometer, and (4) the Wolf Motor Function Test [78] to assess function limitations and allow comparison with the results of CIMT (used as a secondary measure because patients with lower Fugl-Meyer score will not be able to complete many items on this test). Finally, the confirmatory behavior tests listed in Table 1 will be included in the pre-treatment assessment (see B.4 for details). We anticipate that the full pre-treatment screening can be completed in 2 90-minute sessions. De-identified data from both the inclusion screening and pre-treatment assessment will be discussed with the PI before brain scanning is undertaken (C.6) and the patient is assigned to a therapy group

Albert Einstein Healthcare Network <hr/> Einstein	AEHN Protocol/Summary		
	NUMBER	DATE	PAGE
	HRP-204	11/1/2011	11 of 27

(C.7.a) to ensure that the patient meets inclusion criteria and that no unusual combination of scores might suggest errors in data collection or scoring.

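### Aim 3 is restricted to the MT group throughout, so the lesion-to-process tests in C.13.c drop about a third of patients although they use only pre-treatment data

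*Combined protocol and SAP*

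**What the plan says.** C.13 (section 6.g.ii) sets the analysis population for Aim 3 in its first line: "All tests of Specific Aim 3 will focus on data from the MT group only". Three sets of tests follow under that line. C.13.a relates lesion location to post-treatment outcome, C.13.b relates the process tests to post-treatment outcome, and C.13.c relates damage in the Table 1 regions to the process tests themselves. No exception is made for C.13.c.

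The first C.13.c analysis is a t-test of whether the "pre-treatment confirmatory behavioral tests (the only time the tests are administered) will differ as a function of damage status to a particular ROI". The second is a regression of each process score on percent damage to the region, after total lesion volume.

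C.5 (section 6.e.ii) says that for patients who meet the inclusion criteria "the confirmatory behavior tests listed in Table 1 will be included in the pre-treatment assessment". It also says that these data are reviewed "before brain scanning is undertaken (C.6) and the patient is assigned to a therapy group".

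On numbers, section 5.b gives "140 screened in single session, with target of 100 meeting inclusion criteria for the full treatment study". Of these, "approximately 60 will be recruited to the brain imaging" study, and the rest are expected to have research scans already. Neither statement refers to treatment arm. On allocation, C.7.a says "we will assign patients to the MT and placebo treatment groups in a 2:1 ratio, respectively".

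**The concern.** A restriction by treatment arm is useful when the outcome could depend on treatment. In C.13.c it cannot: the process scores and the lesion map both describe the patient before therapy starts. A placebo patient's data answer the question exactly as well as an MT patient's.

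C.13.c is the check that the process tests and the Table 1 regions reflect the same four processes, and the converging-evidence argument in B.4 relies on that link. The protocol also justifies Aim 3 by its large sample and says that earlier studies lacked power (section 2). An analyst who follows the plan as written would leave a third of the available patients out of this check. Placebo patients would have sat the tests, and been asked to have a scan, without contributing to the one analysis for which those data are sufficient.

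**Working it through.** **The plan's own power figure.** The only one in the document is in C.7.a: 2:1 allocation is said to cost about 3% of power. That concerns the comparison between arms. With N = 100 and two-sided 5%, power is approximately Φ(d / √(1/n₁ + 1/n₂) − 1.96). Choosing d to give a set power at 50:50, then recomputing at 66.7:33.3, gives a loss of 4.8 points from 80%, 3.0 points from 93% and 2.5 points from 95%. The figure is therefore plausible. It says nothing about C.13.c, for which no power, effect size or sample size is stated.

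**Can either C.13.c variable depend on arm?**

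| Variable | When obtained | In whom | Source |
|---|---|---|---|
| Process test scores | Before treatment | All patients meeting the criteria | C.5, C.13.c |
| Lesion map | Existing scan, or new scan before therapy | All 100 planned (about 60 new, the rest existing), no restriction by arm | 5.b, 6.c.i, C.5, C.6 |

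Neither can. RASP is repeated later as a primary outcome, but C.13.c uses its pre-treatment score. Because assignment is random, adding the placebo patients introduces no bias.

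**Patients lost.** 100 × 2/3 = 66.7, so about 67 MT patients are used and about 33 placebo patients are left out.

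**Precision.** Standard errors scale with 1/√n. √(100/67) = 1.22, so the planned standard errors are about 22% wider than they need be. Equivalently, √(67/100) = 0.82, so using all patients narrows them by about 18%. This step needs no assumption about effect size.

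**Power, regression.** Assumptions: two-sided 5%, one predictor after one covariate (lesion volume), noncentral F with 1 and n − 3 degrees of freedom and noncentrality n·r²/(1 − r²).

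| Partial r | n = 67 | n = 100 |
|---|---|---|
| 0.20 | 38% | 52% |
| 0.30 | 72% | 88% |
| 0.40 | 94% | 99% |

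A Fisher-z approximation, Φ(atanh(r)·√(n − 4) − 1.96), is slightly lower at r = 0.30: 69% against 86%.

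**Power, t-test by region damage.** Assumptions: two-sided 5%, 20% of patients meeting the damage criterion, so 13 v 54 (MT only) or 20 v 80 (all). Noncentrality is d·√(n₁n₂/(n₁ + n₂)); at d = 0.8 this is 2.59 and 3.20.

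| d | 13 v 54 | 20 v 80 |
|---|---|---|
| 0.5 | 36% | 51% |
| 0.65 | 54% | 73% |
| 0.8 | 72% | 89% |
| 1.2 | 97% | 99.7% |

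Over d from 0.5 to 0.8 and damaged shares from 10% to 50%, the loss is about 8 to 19 points.

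**Fewer usable scans.** If scans are missing equally across arms, the proportional loss is the same but falls on smaller numbers. With 60 usable maps in all, power at r = 0.30 is 49% (n = 40) against 67% (n = 60).

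**The case against.** The best defence is that the opening line was written with prediction of benefit in mind, as the C.13 heading suggests, and was carried over to part c by oversight. The verb is a soft one, the placebo data are collected anyway, and they could be analysed in full later. C.13.c is also a supporting check: it does not estimate the effect of MT, the dosing pattern or the prediction of benefit. All of that is fair and limits how much is at stake. It does not remove the point. The line covers every Aim 3 test and admits no other patients, and changing the population after the data are seen would be a post hoc choice.

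The power figures depend on assumed effects. If the associations are strong (r = 0.40 or d = 1.2) both sample sizes suffice, and at r = 0.20 both fall well short of 80%. That stands. The lost third and the 22% do not depend on it.

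The count of 33 is a ceiling, because patients may decline a new scan (section 6.a.i). That also stands, although the proportion lost is unchanged if scans are missing equally in both arms.

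One process measure, the rating of the initial mirror illusion, might not exist for patients who train with an opaque divider. C.5 places all Table 1 tests before assignment, so it should exist, but the test list in section 6.e.iii does not mention it. This is worth confirming and leaves the other measures untouched.

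Finally, MT-only analysis in C.13.a and C.13.b can itself be questioned, since without a comparator a predictor of MT benefit cannot be told apart from a general predictor of later score. That is a separate matter. Optional crossover of placebo patients does not help either: the plan does not say that they join the MT group for Aim 3, and their C.13.c data exist before assignment.

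**Conclusion.** The concern holds, for C.13.c only. The MT-only rule removes about 33 of 100 patients from tests on which treatment has no bearing, and widens standard errors by about 22% with no gain in validity. This rests on the target of 100, on 2:1 allocation, and on usable lesion maps being equally available in both arms. The cost in power is illustrative: about 16 points at a partial correlation of 0.30, or at d = 0.8 with 20% of patients damaged, and less where the effect is strong. The harm is lost precision in a supporting analysis. Aim 1 is unaffected and nothing is biased. It is worth correcting because the correction costs almost nothing.

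**What to change.** Replace the opening line of C.13 with:

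> Tests in C.13.a and C.13.b use the MT group. Tests in C.13.c use all randomised patients with a pre-treatment assessment and a usable lesion map, regardless of assigned therapy.

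This leaves the plan's present rule for C.13.a and C.13.b as it is. At the same time, confirm that the illusion rating is taken from every patient before assignment.

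The cost is one sentence. No extra data, visits or staff are needed, because the placebo patients' tests and lesion maps are already planned. The change should be made before Aim 3 is analysed, so that the population is fixed in advance.
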